12.0 STATISTICAL CONSIDERATIONS

12.1 Hypothesis

Our primary hypothesis is that fostamatinib alone and in combination with ruxolitinib will provide a safe and tolerable treatment in patients with myelofibrosis with severe thrombocytopenia (platelet < 50K/microL). Treatment with fostamatinib will improve thrombocytopenia in patients with myelofibrosis with severe thrombocytopenia (platelet < 50K/microL) and allow them to initiate treatment with ruxolitinib.

12.2 Study Design

This is a hypothesis generating limited pilot phase II study evaluating the efficacy and safety of the use of fostamatinib as a single agent and when given in combination with ruxolitinib in patients with intermediate to high risk myelofibrosis. Previous studies with fostamatinib and ruxolitinib monotherapy indicate that toxicity will be low grade and reversible with standard treatment.

This study consists of two parts. For Part A, patients with MF and severe thrombocytopenia will initially receive 12 weeks of single agent fostamatinib and the primary endpoint will be platelet response (defined as platelet count of $\geq 50K/\text{microL}$ as two separate measurements at least two weeks apart) at the end of the 12 week treatment period. Patients who achieve a sustained platelet response will then be eligible to proceed to Part B of the study and begin treatment with ruxolitinib while continuing to take fostamatinib. For Part B, patients will continue treatment with fostamatinib and ruxolitinib for up to an additional 36 weeks and the primary endpoint will be safety as assessed by NCI CTCAE v 5.0. Patients who do not have a sustained platelet response after 12 weeks of treatment but are clinically benefiting from fostamatinib may remain on Part A of the study and be eligible to enroll in Part B if they achieve a sustained platelet response prior to Day 1 Cycle 10 of treatment.

A maximum of 12 patients will be enrolled. A Bayesian sequential monitoring rule will be implemented for safety.

Safety monitoring (Part B): The stopping rule is defined as $\text{Pr}(\theta > \theta_T | \text{data}) > 0.8$, where θ denotes the proportion of AEs of interest as defined in Section 5.5 and θ_T denotes the rate of AEs of interest under the null hypotheses (i.e., 20% AEs of interest). That is, an early termination of the study due to excessive toxicities will be recommended whenever, given the accumulated observed data, there is high chance (i.e., >80% probability) for the “true” AEs of interest rate >20%. The stopping boundaries were obtained using Multc99 version 2.1, a free-download software from M.D. Anderson Cancer Center. Specifically, we assume that the parameter θ follows a prior distribution of beta (0.2, 0.8), i.e., θ with mean = 0.2 but with relatively large variability (non-informative prior). Early stopping will be recommended if we observe 3 patients who experience AEs of interest out of first 5 patients

or 4 patients who experience AEs of interest out of first 9 patients. A simulation study was also performed to assess the operating characteristics for the above stopping rule (all scenarios are based on 10,000 simulated trials). If the “true” AEs of interest rate is 10%, there will be only 4% chance to stop. In contrast, we will have 76% chance to stop if the “true” rate is 40%.

# Patients treated	1	2	3	4	5	6	7	8	9	10	11	12
Stop if the # AEIs \geq	N/A	N/A	N/A	N/A	3	3	3	3	4	4	4	4

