2.0 OBJECTIVES AND ENDPOINTS

2.1 Part A Objectives and Endpoints

Objectives	Endpoints	Justification for Endpoints
Primary		
To evaluate the impact of fostamatinib on platelet counts in patients with myelofibrosis and severe thrombocytopenia	Platelet response as detailed in Section 11.2.2, platelet response by week 12 and end of fostamatinib monotherapy treatment, and number of patients eligible to initiate treatment with a JAK2 inhibitor (ruxolitinib)	The efficacy of fostamatinib on thrombocytopenia in MF patients is unknown
Secondary		
To evaluate the safety and tolerability of single agent fostamatinib in patients with MF and thrombocytopenia	Incidence, severity, frequency, and outcomes of AEs and SAEs as defined by CTCAE v5.0 criteria, AEIs, laboratory abnormalities, and number of patients who permanently discontinue fostamatinib due to fostamatinib-related AEs, number of patients who require treatment interruptions due to fostamatinib-related AEs	The safety and tolerability of fostamatinib in MF patients is unknown.
To evaluate spleen response in patients with MF receiving fostamatinib	Spleen response as detailed in Section 11.4 at week 12 and end of fostamatinib monotherapy treatment, mean reduction in spleen volume as determined by ultrasound at week 12 and end of fostamatinib monotherapy treatment	The efficacy of fostamatinib on reducing spleen size in MF patients is unknown
To evaluate anemia response in patients with MF receiving fostamatinib	Anemia response as detailed in Section 11.2.1	The impact of fostamatinib on anemia in MF patients is unknown

To evaluate the impact of fostamatinib on constitutional symptoms in patients with MF	Constitutional symptoms as detailed in Section 11.3 at week 12 and end of fostamatinib monotherapy treatment	The efficacy of fostamatinib on improving symptoms in MF patients is unknown
To evaluate the impact of fostamatinib on transfusion requirements	Number of patients who achieve platelet and RBC transfusion independence who were previously requiring transfusions	The impact of fostamatinib on transfusion burden in MF patients is unknown
To evaluate the impact of fostamatinib on marrow fibrosis	Change in marrow fibrosis per WHO grading on bone marrow biopsy performed at the end of fostamatinib monotherapy	The impact of fostamatinib on marrow fibrosis is unknown

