2.2 Part B Objectives and Endpoints

Objectives	Endpoints	Justification for Endpoints
Primary		
To evaluate the safety and tolerability of the combination of fostamatinib and ruxolitinib in MF patients	Incidence, severity, frequency, and outcomes of AEs and SAEs as defined by CTCAE v5.0 criteria and AEs of interest (AEIs) as defined in section 5.5	The safety of this combination therapy in MF patients is not known.
Secondary		
To evaluate the spleen response in patients with MF receiving fostamatinib in combination with ruxolitinib	Spleen response as detailed in Section 11.4 after 12 weeks of combination therapy, mean reduction in spleen volume as determined by ultrasound after 12 weeks of combination therapy and at the end of treatment	The efficacy of fostamatinib in combination with a JAK inhibitor on reducing spleen size in patients with MF is unknown
To evaluate the impact of fostamatinib in combination with ruxolitinib on constitutional symptoms in patients with MF	Constitutional symptoms as detailed in Section 11.3 after 12 weeks of combination therapy and at the end of treatment	The efficacy of fostamatinib in combination with a JAK inhibitor on symptoms in MF is unknown
Evaluate the ability of fostamatinib to enable sustained treatment with ruxolitinib	Duration of uninterrupted JAK inhibitor (ruxolitinib) therapy	The ability of fostamatinib to maintain an adequate platelet count for patients

		to remain on JAK inhibitor therapy is unknown
To evaluate the impact of fostamatinib and ruxolitinib on marrow fibrosis	Change in marrow fibrosis per WHO grading on bone marrow biopsy performed at the end of fostamatinib and ruxolitinib therapy	The impact of fostamatinib and ruxolitinib combination therapy on marrow fibrosis is unknown

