5.4 Toxicity Monitoring (Stopping Rules)

A Bayesian sequential monitoring rule will be used to protect patients from excessive toxicities (see Section 12.2 for technique details), and the table below shows the boundaries of early stopping rule. That is, an early stopping of the study due to excessive toxicities will be recommended if we observe 3 patients who experienced AEs of interest (as defined in Section 5.5) out of the first 5 patients or 4 patients who experience AEs of interest out of first 9 patients.

# Patients treated	1	2	3	4	5	6	7	8	9	10	11	12
Stop if the # AEIs \geq	N/A	N/A	N/A	N/A	3	3	3	3	4	4	4	4

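### Section 12.2 labels the stopping rule for adverse events of interest as Part B, Section 5.4 applies the same table to all treated patients, and the stated 76% chance of stopping needs 11 or 12 patients

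*Combined protocol and SAP*

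**What the plan says.** Section 12.2 first announces the rule without limiting it: "A Bayesian sequential monitoring rule will be implemented for safety". That follows "A maximum of 12 patients will be enrolled". The next paragraph then opens with "Safety monitoring (Part B): The stopping rule is defined as" and sets the criterion: a posterior probability above 0.8 that the AEI rate exceeds 20%, under a beta (0.2, 0.8) prior. The section reports a simulation of 10,000 trials: a 4% chance of stopping at a true AEI rate of 10%, and "we will have 76% chance to stop if the" true rate is 40%.

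Section 5.4 prints the same boundaries: 3 AEI patients once 5 to 8 have been treated, 4 once 9 to 12 have been treated, none before 5. It says "an early stopping of the study due to excessive toxicities will be recommended if we observe 3 patients who experienced AEs of interest" among the first 5, or 4 among the first 9. It names no part of the study and sends the reader to Section 12.2 only for technique.

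Other text supports each reading.
- **Whole study:** Section 5.5 counts events related to either drug. Section 2.1 lists "AEs and SAEs as defined by CTCAE v5.0 criteria, AEIs, laboratory abnormalities" among the Part A safety endpoints. Section 5.6 makes every treated patient evaluable for toxicity. Section 12.4 counts AEIs out of 12.
- **Part B only:** the label itself. Section 12.2 also says that for Part B "the primary endpoint will be safety as assessed by NCI CTCAE v 5.0", and Section 2.2 includes "AEs of interest (AEIs) as defined in section 5.5" in that primary endpoint.

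**The concern.** A stopping rule needs one denominator, and here the same data can give opposite answers. Suppose 3 of the first 5 treated patients have an AEI during fostamatinib monotherapy. Section 5.4 recommends stopping the study. Under the Section 12.2 label those patients are not counted, and Part A has no boundary at all.

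The label also affects the reported performance of the rule. Under Section 5.3, only patients with a sustained platelet count of at least 50,000/microL move to Part B, so Part B will probably be smaller than 12. If only those patients count, the rule cannot trigger until 5 have entered, and the quoted 76% may not describe it. Section 11.0 requires the semi-annual report to the safety committee to list stopping-rule status, which cannot be done consistently while the denominator is open.

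**Working it through.** **Inputs from the documents.** Prior beta (0.2, 0.8), reference rate 20%, threshold 0.8, stated results 4% and 76%, maximum 12 patients (Section 12.2). Boundaries of 3 at n = 5–8 and 4 at n = 9–12 (Sections 5.4 and 12.2).

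**Assumptions.** AEIs are independent between patients and each patient counts once. The documents give no Part B entry rate. I use 20% and 40%, the illustrative platelet response rates in Section 12.4, and 50% and 60% to allow for late entry before Cycle 10 Day 1.

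**Step 1: the boundaries.** With x AEI patients among n, the posterior is Beta(0.2 + x, 0.8 + n − x). Pr(rate > 0.2) is:
- n = 5: 0.797 for x = 2, 0.960 for x = 3
- n = 8: 0.572 for x = 2, 0.838 for x = 3
- n = 9: 0.785 for x = 3, 0.934 for x = 4
- n = 12: 0.613 for x = 3, 0.829 for x = 4

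The printed boundaries from n = 5 to 12 follow.

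**Step 2: the stated 4% and 76%.** The chance of stopping by patient n is found by carrying forward the probability of each AEI count among trials not yet stopped. At a true rate of 0.4:
- n = 5: P(X ≥ 3) = 0.2304 + 0.0768 + 0.0102 = 0.3174
- n = 6: add P(2 of 5) × 0.4 = 0.3456 × 0.4 = 0.1382, giving 0.4557
- n = 7: add P(2 of 6) × 0.4 = 0.3110 × 0.4 = 0.1244, giving 0.5801
- n = 8: add P(2 of 7) × 0.4 = 0.2613 × 0.4 = 0.1045, giving 0.6846
- n = 9: no addition, because an unstopped trial has at most 2 AEIs at n = 8 and needs 4

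Continuing, with every printed look applied:

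| Patients counted | Stop, AEI rate 10% | Stop, AEI rate 40% |
|---|---|---|
| 4 or fewer | 0% | 0% |
| 5 | 0.9% | 31.7% |
| 6 | 1.6% | 45.6% |
| 7 | 2.6% | 58.0% |
| 8 or 9 | 3.8% | 68.5% |
| 10 | 4.0% | 71.8% |
| 11 | 4.3% | 76.4% |
| 12 | 4.7% | 81.1% |

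The stated 4% and 76% match the row for 11. Twelve patients with looks after patients 5 to 11 is the same stopping event, since a stop at the last patient would not be early. Counting the printed look at 12 gives 81.1%. The simulation error at 0.76 is √(0.76 × 0.24 / 10,000) ≈ 0.004, so 76% against 81% is not noise. Other schedules fit worse (40% / 10% AEI rate): looks at 5 and 9 only give 54.7% / 1.4%, and the posterior rule applied from the first patient gives 85.5% / 14.5%.

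**Step 3: Part B only.** Let the number entering be K ~ Binomial(12, r), and average the 40% column over K. For r = 0.4:

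0.2270 × 0.3174 + 0.1766 × 0.4557 + 0.1009 × 0.5801 + 0.0420 × 0.6846 + 0.0125 × 0.6846 + 0.0025 × 0.7180 + 0.0003 × 0.7639 ≈ 0.250

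| Assumed entry rate r | P(K ≥ 5) | P(K ≥ 11) | Average chance of stopping, AEI rate 40% |
|---|---|---|---|
| 20% | 7% | <0.001% | 2.6% |
| 40% | 56% | 0.03% | 25% |
| 50% | 81% | 0.3% | 41% |
| 60% | 94% | 2.0% | 55% |

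The average is 70.8% at r = 0.8 and 75.7% at r = 0.9. It reaches 76% at r of about 0.91.

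**The case against.** The best reply is that the Part B label is simply misplaced. Section 5.4 is the operational section and is unrestricted. Section 12.2 itself speaks of terminating the study. Section 5.6 makes all treated patients evaluable for toxicity, Section 12.4 uses 12 as the AEI denominator, and the simulated figures fit a 12-patient trial. On that reading 4% and 76% are right and the Part B calculations describe a rule nobody intended. Those calculations also rest on entry rates the protocol does not give.

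Much of this stands. The text leans towards the whole study, and the averaged Part B figures are conditional on assumed entry rates. It does not remove the conflict. Section 5.6 never mentions the stopping rule, and the label sits at the head of the paragraph that defines it, for the part of the study whose primary endpoint is safety. A team following Section 12.2 as written would leave Part A events out. The central numerical point needs no entry rate: fewer than 5 counted patients gives 0%, and 76% is first reached at 11.

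It is also fair that the documents do not describe the look schedule behind the 76%. The schedule given here is inferred from the match, and the sponsor can check it against its simulation output.

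Finally, Part A patients are not unprotected under either reading: ongoing toxicity monitoring (Section 11.0), individual discontinuation criteria (Section 5.10) and dose-modification rules (Section 6.1) still apply.

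**Conclusion.** The concern holds and should be fixed. Sections 5.4 and 12.2 give the same stopping table two different scopes, and nothing in the protocol settles which governs. The stated 76% is correct for 12 patients with looks after patients 5 to 11, but it does not describe a Part B-only rule unless about 11 of the 12 patients enter Part B. With 5 to 10 Part B patients the chance of stopping at a 40% AEI rate is 32% to 72%; averaged over assumed entry rates of 20% to 60% it is 2.6% to 55%. The 4% is less sensitive, at 3.8% to 4.3% with 8 to 11 patients. These results assume independent AEIs with each patient counted once. The averages also need the assumed entry rates; the results by cohort size do not. This is an inconsistency of text, not a failure of the monitoring design.

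**What to change.** Reconcile Sections 5.4 and 12.2 on one denominator. The choice is the sponsor's.

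- **Option 1, whole study.** Delete the Part B label in Section 12.2. State in both sections that the table counts all treated patients across Parts A and B, each once. State that 4% and 76% refer to 12 patients with looks after patients 5 to 11. If the printed look at patient 12 will be used, the matching figures are 4.7% and 81.1%.
- **Option 2, Part B only.** State in Section 5.4 and in the row heading of the table in both sections that only Part B patients count. Replace 4% and 76% with operating characteristics over plausible Part B sizes, using every printed look.

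Option 1 costs wording only. Option 2 also needs a short re-run of the simulation. Neither changes the boundaries, sample size or visits.

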12.3 Analysis Plan

All data analyses will be descriptive in nature. Demographic and clinical characteristics of the sample, as well as response to treatment, and loss to follow up will be summarized using descriptive statistics. Rate of AEs, overall response rate, hematologic response rate, symptom response rate, and spleen response rate will be documented with exact 95% confidence intervals.

12.4 Sample Size and Study Power

A total of 12 patients will be enrolled. As a pilot phase II study for hypothesis generating, formal power calculations to determine sample size were not performed. Based on simulation studies regarding the sample size for translational studies, however, Piantadosi recommends that a sample size of 10 to 20 patients be adequate to provide preliminary information [33]. For efficacy, for example, the probability of observing at most 1 platelet response out of 12 patients is 27% given that the true rate is 20%. However, the probability of observing at least 2 platelet responses is 98% given that the true is 40%. For safety, if the “true” AEs of interest rate is 20% or higher, there will be more than 93% chance to observe at least 1 patient with AE of interest out of 12 patients. Conversely, there is less than 2% chance to observe 3 or more patients with AE of interests if the “true” rate is 5% or less.

APPENDIX A: ECOG Performance Status Scale

Grade	Description
0	Normal activity. Fully active, able to carry on all pre-disease performance without restriction.
1	Symptoms, but ambulatory. Restricted in physically strenuous activity, but ambulatory and able to carry out work of a light or sedentary nature (e.g., light housework, office work).
2	In bed <50% of the time. Ambulatory and capable of all self-care, but unable to carry out any work activities. Up and about more than 50% of waking hours.
3	In bed >50% of the time. Capable of only limited self-care, confined to bed or chair more than 50% of waking hours.
4	100% bedridden. Completely disabled. Cannot carry on any self-care. Totally confined to bed or chair.
5	Dead.

APPENDIX B: PATIENT'S MEDICATION DIARY

Today's Date: _____ Agent: fostamatinib Cycle: _____ Study ID#: _____

1. Complete one form for each month. Take _____ mg (_____ capsules) of fostamatinib twice daily with or without food at approximately the same time each day.
2. Record the date, the number of capsules taken, and when you took them.
3. If you forgot to take your dose, do not make up that dose, but restart taking it with your next scheduled dose.
4. If you have any questions or notice any side effects, please record them in the comments section. Record the time if you should vomit.
5. Please return the forms to your physician or your study coordinator when you go to your next appointment. Please bring your unused study medications and/or empty bottles with you to each clinic visit so that a pill count can be done.

Day	Date	What time was dose taken?		# of tablets taken		Comments
		AM	PM	AM	PM	
1						
2						
3						
4						
5						
6						
7						
8						
9						
10						
11						
12						
13						
14						
15						
16						
17						
18						
19						
20						
21						
22						
23						
24						
25						
26						
27						
28						
29						
30						
31						

APPENDIX C: PATIENT'S MEDICATION DIARY

Today's Date: _____ Agent: ruxolitinib Cycle: _____ Study ID#: _____

1. Complete one form for each month. Take _____ mg (_____ capsules) of ruxolitinib twice daily with or without food at approximately the same time each day.
2. Record the date, the number of capsules taken, and when you took them.
3. If you forgot to take your dose, do not make up that dose, but restart taking it with your next scheduled dose.
4. If you have any questions or notice any side effects, please record them in the comments section. Record the time if you should vomit.
5. Please return the forms to your physician or your study coordinator when you go to your next appointment.

Day	Date	What time was dose taken?		# of tablets taken		Comments
		AM	PM	AM	PM	
1						
2						
3						
4						
5						
6						
7						
8						
9						
10						
11						
12						
13						
14						
15						
16						
17						
18						
19						
20						
21						
22						
23						
24						
25						
26						
27						
28						
29						
30						
31						

APPENDIX D: Definitions for Adverse Event Reporting

A. Adverse Events (AEs)

As defined in 21 CFR 312.32:

Definition: any untoward medical occurrence associated with the use of a drug in humans, whether or not considered drug-related.

Grading: the descriptions and grading scales found in the revised NCI Common Terminology Criteria for Adverse Events (CTCAE) version 5.0 will be utilized for all toxicity reporting. A copy of the CTCAE version 5.0 can be downloaded from the CTEP website.

Attribution (relatedness), Expectedness, and Seriousness: the definitions for the terms listed that should be used are those provided by the Department of Health and Human Services' Office for Human Research Protections (OHRP). A copy of this guidance can be found on OHRP's website:

<http://www.hhs.gov/ohrp/policy/advevntguid.html>

B. Suspected Adverse Reaction (SAR)

As defined in 21 CFR 312.32:

Definition: any adverse event for which there is a reasonable possibility that the drug caused the adverse event. “Reasonable possibility” means there is evidence to suggest a causal relationship between the drug and the adverse event. “Suspected adverse reaction” implies a lesser degree of certainty about causality than adverse reaction, which means any adverse event caused by a drug.

C. Life-Threatening Adverse Event / Life Threatening Suspected Adverse Reaction

As defined in 21 CFR 312.32:

Definition: any adverse drug event or suspected adverse reaction is considered “life-threatening” if, in the view of the investigator, its occurrence places the patient at immediate risk of death. It does not include an adverse event or suspected adverse reaction that, had it occurred in a more severe form, might have caused death.

D. Serious Adverse Event (SAE) or Serious Suspected Adverse Reaction

As defined in 21 CFR 312.32:

Definition: an adverse event or suspected adverse reaction is considered “serious” if, in the view of the investigator, it results in any of the following outcomes:

- Death
- A life-threatening adverse event

- Inpatient hospitalization or prolongation of existing hospitalization
- A persistent or significant incapacity or substantial disruption of the ability to conduct normal life functions
- A congenital anomaly/birth defect
- Any other important medical event that does not fit the criteria above but, based upon appropriate medical judgment, may jeopardize the subject and may require medical or surgical intervention to prevent one of the outcomes listed above

The terms “severe” and “serious” are not synonymous. Severity (or intensity) refers to the grade of an AE. “Serious” is a regulatory definition.

A serious adverse event (experience) or reaction is any untoward medical occurrence that at any dose:

- Results in death;
- Is life-threatening. (With regards to determining if an AE is serious, “life-threatening” is defined as an AE in which the subject was at risk of death at the time of the event. It does not refer to an event which hypothetically might have caused death if it were more severe. If either the investigator or the Sponsor believes that an AE meets the definition of life threatening, it will be considered life-threatening);
- Requires in-patient hospitalization or prolongation of an existing hospitalization;
- Results in persistent or significant disability/incapacity (e.g., the AE results in substantial disruption of the subject’s ability to conduct normal life functions); or
- Is a congenital anomaly/birth defect;
- Is considered an important medical event (or medically significant) that may not result in any of the above outcomes but based upon appropriate medical judgment, may jeopardize the subject and may require medical or surgical intervention to prevent one of the outcomes listed

Medical and scientific judgment should be exercised in deciding whether other situations, such as important medical events, should also be considered serious. Some examples of such events are intensive treatment in an emergency room or at home for allergic bronchospasm; blood dyscrasias, or convulsions that do not result in hospitalization; or development of drug dependency or drug abuse. Given that the investigator’s perspective may be informed by having actually observed the event and Rigel is likely to have broader knowledge of the study drug and its effects to inform its evaluation of the significance of the event, if either Rigel or the investigator believes that the event is serious, the event will be considered an important medical event.

E. Protocol Exceptions

Definition: A planned change in the conduct of the research for one participant.

F. Deviation

Definition: Any alteration or modification to the IRB-approved research without prospective IRB approval. The term “research” encompasses all IRB-approved materials and documents

including the detailed protocol, IRB application, consent form, recruitment materials, questionnaires/data collection forms, and any other information relating to the research study.

A minor or administrative deviation is one that does not have the potential to negatively impact the rights, safety, or welfare of participants or others or the scientific validity of the study.

A major deviation is one that does have the potential to negatively impact the rights, safety, or welfare of participants or others or the scientific validity of the study.

